## **Study Protocol**

**Recruitment.** Participants were recruited nationwide through advertisements and physician referrals. Specifically, recruitment techniques included electronic media (e.g., university listservs, social media, websites, craigslist) and flyers in community-based organizations (e.g., campus, community health centers).

**Pilot Procedure.** Interested individuals completed a phone pre-screen. Individuals who were eligible at the pre-screen and willing to participate in the study were contacted and scheduled for an in-person baseline appointment at the laboratory, wherein full eligibility was assessed, and informed consent was completed. At the in-person baseline appointment, participants were provided informed consent and completed additional eligibility screening, including (1) a preintervention online eligibility survey (~90 minutes) and (2) and measures administered by a trained research assistant (e.g., CO assessment, breath holding tasks; ~20 minutes). Following completion of these tasks, a trained research assistant determined the participant's eligibility. Subjects deemed ineligible were unable to participate in the intervention, provided with resources, and compensated \$10 for their time. Participants deemed eligible completed a computer delivered intervention (~ 90 minutes) of the Active personalized feedback intervention (PFI). Following the intervention, participants completed a post-intervention online survey (~15 minutes) and tasks with a trained research assistant (~5 minutes). Additionally, participants completed an individual semi-structured interview with a trained researcher (~10 minutes). The semi-structured interview included questions about the personalized feedback format and content, and suggestions to improve the feedback. The investigative team reviewed the feedback from the first 5 eligible participants and adapted/refined the intervention content as needed. We then present a revised version of the PFI to an additional 5 eligible participants individually, and completed the same feedback/evaluation process. Changes and suggestions elicited from the second round of participants were integrated into the final PFI to be tested in the RCT phase. Participants were compensated \$60 for their time.

**RCT Procedure.** Interested participants were instructed to contact the research lab. Participants who expressed interested were sent a unique link to an online survey which included demographic and selected eligibility screening questions (e.g., cigarettes smoked per day, distress tolerance) that took approximately 10 minutes to complete. Each unique link could only be used one time. Individuals who were eligible at the pre-screen and willing to participate in the study were provided an additional unique link to complete an online baseline assessment. During the baseline assessment, informed consent was obtained electronically. The participant then completed an approximately 90-minute pre-intervention online survey that further evaluated eligibility criteria (i.e., re-evaluated distress tolerance) as well as assessed psychological and health-related constructs of interests. Participants who did not meet eligibility criteria were provided with referrals and compensated \$10 in the form of an electronic gift card. To ensure quality responses, speeding checks were included and IP addresses and coordinates were checked to prevent multiple attempts to complete the survey by the same respondent. Moreover, unique links to participate were created for each participant at every stage of the study. Participants who met eligibility criteria were randomly assigned to complete either the (a) Active PFI (60-minutes) or (b) Control PFI (30-minutes). Following the completion of the program, participants were redirected to complete a post-intervention online survey (~15-minutes) to gather qualitative feedback and assess for treatment satisfaction. Eligible participants were compensated \$60 in the form of an electronic gift card upon completing all portions of the

baseline (e.g., pre-intervention survey, randomly assigned intervention, and post-intervention survey). Participants were then emailed a unique link to complete an online assessment at 2-weeks and 1-month post-intervention to assess relevant psychological and health-related constructs of interest. The post-intervention online assessments took approximately 30-minutes (each) to complete. Participants were compensated with \$30 in electronic gift cards for completing each of the follow-up assessments for up to \$120 in electronic gift cards for completing the entirety of the study.

## Randomized Clinical Trial (RCT) Procedure:

Control PFI Condition: The Control PFI included personalized feedback on motivation to change smoking, behavior through eliciting responses regarding importance, confidence, and readiness to quit smoking. Next participants were shown graphics depicting their perceptions of smoking behaviors (e.g., percentage of sex-matched adults who they believe currently smoke) and attitudes (e.g., percentage of individuals who they believe smoke that would like to quit) in comparison to normative values in the US. Participants were then guided through a variety of financial and health-related costs of smoking personalized to their smoking behavior (e.g., amount they spend on cigarettes, impact on life expectancy) as well as psychoeducation on dangerous chemicals currently used in cigarettes. Participants were also provided with various health benefits of quitting smoking. Finally, quit tactics were reviewed with participants (e.g., gradual reduction, nicotine replacement therapy) as well as the 5 D's (i.e., Delay, Distract, Deep breaths, Drink water, and Discuss). The intervention included a racial/ethnic and sex-matched digital avatar that guided participants through the intervention. The Control PFI also provided audio and visual aspects to portray the relevant information and interactive games and activities to foster engagement.

Active PFI Condition: The Active PFI included all of the components of the Control PFI as well as the addition of distress tolerance components. Distress tolerance components included personalized normative feedback about distress tolerance and its consequences. For example, participants were provided psychoeducation on what low distress tolerance is, what it can lead to (e.g., worsened mental health), and how their distress tolerance level compares to normative averages. Next, participants were provided psychoeducational information regarding relations between distress tolerance and smoking behavior (e.g., how distress tolerance influences smoking behavior). Finally, concrete evidenced-based strategies to encourage motivation and action steps for changing distress tolerance taken from intensive distress tolerance treatments were incorporated. Specifically, participants engaged in imaginal activities aimed at building tolerance for distress such as imagining a recent stressful event and imagining being around cigarette smoke. Participants were encouraged to continue to practice imaginal activities in order to build tolerance to distress.

## **Statistical Analysis Plan**

The equivalence of the random assignment of groups regarding key baseline characteristics (e.g., demographics) and retention (i.e., 2-week, 1-month; 0 = completed and 1 = missed) were assessed. Differences between key baseline characteristics were also assessed for participants who completed all follow-ups (coded 0) versus participants who missed at least one follow-up (coded 1). Then, paired t-tests were conducted to assess change in credibility and expectancy between baseline and post-intervention. Latent growth curve (LGC) analyses were then conducted using Mplus version 8.6 using maximum likelihood. Multiple imputation using

1,000 imputed datasets calculated in Mplus were used to handle missing data. LGC modeling was used to evaluate the overall trajectories across time of smoking related variables: (1) increased motivation, confidence, and intention to quit, (2) fewer perceived barriers for quitting smoking, and (3) reduced smoking rate. A conditional model was then specified to examine the impact of treatment (0 = Control PFI, 1 = Active PFI) on the slope factor for each of the stated outcome variables. Similar procedures were utilized for mood-related outcomes: (1) greater distress tolerance, (2) reductions in anxiety/depressive symptoms, and (3) increased willingness to use adaptive coping strategies.

For all analyses, shape factors were set for the slope to be centered at the baseline assessment and the 1-month follow-up was fixed at 1.0. The 2-week follow-up was freely estimated. LGC analysis model fit was evaluated with the following fit indices: root-mean-square (RMSEA; Steiger, 1990) and standardized root-mean-square residual (SRMR; Jöreskog & Sörbom, 1996) with values below .08 indicating acceptable fit (Little, 2013), Tucker-Lewis index (TLI; Tucker & Lewis, 1973) and comparative fit index (CFI; Bentler, 1990) with values at .90 or above indicating acceptable fit (Little, 2013). Effect sizes were interpreted in the Cohen's d metric (i.e., small = 0.2, medium = 0.5, and large = 0.8) utilizing the partially standardized path coefficient.

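### With three waves and a free 2-week loading, the unconditional growth model has df = 0, so its fit cut-offs cannot fail; and the treatment-on-slope path is in general not the 1-month arm difference

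*Combined protocol and SAP*

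**What the plan says.** The Statistical Analysis Plan gives a two-stage growth analysis. First, "LGC modeling was used to evaluate the overall trajectories across time of smoking related variables"; this covers motivation, confidence and intention to quit, barriers to quitting, and smoking rate. Then "A conditional model was then specified to examine the impact of treatment", coded 0 for Control PFI and 1 for Active PFI, "on the slope factor for each of the stated outcome variables". The second outcome family is handled alike: "Similar procedures were utilized for mood-related outcomes", namely distress tolerance, anxiety/depressive symptoms and willingness to use adaptive coping.

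For every analysis the slope is centred at baseline, and "the 1-month follow-up was fixed at 1.0. The 2-week follow-up was freely estimated". On fit, "LGC analysis model fit was evaluated with the following fit indices": RMSEA and SRMR "with values below .08 indicating acceptable fit", and TLI and CFI acceptable from .90 upwards. No distinction is made between the unconditional and the conditional model. The slope path, standardised on the outcome side only, is read on the scale of Cohen's d. On missing data, "1,000 imputed datasets calculated in Mplus were used to handle missing data".

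The section states no degrees of freedom, no constraint on residual or factor variances, and no arm contrast at a single visit. It does not say whether treatment also predicts the intercept. It does not describe the slope path as a 1-month effect.

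**The concern.** Two things follow from the loading pattern.

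First, a three-wave growth model that spends a parameter on the middle loading may have nothing left to test. Acceptable fit of the model used for the overall trajectories would then be a property of the specification, not of the data, and reporting it as support for the trajectories would mislead.

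Second, the conditional model makes both arms follow one time shape. With the 1-month loading set to 1.0 and the path read as a Cohen's d, a reader will easily take it for the arm difference at the end of the study. If the arms' courses differ in shape, the path mixes the 2-week and 1-month differences. An effect that has faded by 1 month could then be described as though it were still present at that size.

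**Working it through.** **Inputs.** From the RCT Procedure: baseline, 2 weeks and 1 month, hence three waves. The immediate post-intervention survey covers feedback and satisfaction, and the SAP gives it no loading. From the SAP: loadings 0, λ (free) and 1.0; maximum likelihood; the four fit cut-offs. The documents give no sample size, means, correlations or df, so there is no stated figure to reproduce.

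**1. Unconditional model.**
- Moments: 3 means + 6 variances and covariances = 9.
- Parameters: 2 growth means + 2 growth variances + 1 growth covariance + 3 residual variances + 1 free loading = 9.
- df = 9 − 9 = 0. The Jacobian of the model moments has rank 9, so the model is just-identified. If the mean change to 1 month is exactly zero, the rank is 8 and λ is not identified.
- If the 3 residual variances are held equal, 2 parameters drop and df = 2.

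For any λ other than 0 or 1, the six covariance parameters reproduce the six variances and covariances. λ is therefore set by the means alone: λ = (2-week change)/(1-month change). Three very different mean paths are each reproduced exactly:
- 0, .25, .5: λ = .25/.5 = .5
- 0, .9, .3: λ = .9/.3 = 3.0
- 0, −.4, .3: λ = −.4/.3 = −1.33

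So RMSEA = 0, SRMR = 0 and CFI = 1 whatever the data show, unless a variance is held at a bound. TLI carries no information.

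**2. Conditional model.** Treatment adds 3 moments (its relation to each wave): 9 + 3 = 12. Parameters: 9 + 1 = 10 if treatment predicts the slope only, or 9 + 2 = 11 if it also predicts the intercept. So df = 2 or 1 (4 or 3 with equal residual variances). Fit is informative here.

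**3. What the slope path estimates.** Let C2 and C3 be the control arm's mean changes at 2 weeks and 1 month, and D2 and D3 the arm differences in change. The model says C2 = λC3 and D2 = λD3. That is four quantities and three parameters, hence one restriction: D2·C3 = D3·C2, meaning proportional courses. An unchanged control arm (C2 = C3 = 0) satisfies it. If it fails, the version with both treatment paths gives slope path = w2·D2 + w3·D3 with λ·w2 + w3 = 1, where the weights depend on the covariances. The path then equals D3 only by coincidence.

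An example with all correlations .5 and an effect at 2 weeks only (D2 = .40, D3 = 0): λ = 1.15, w2 = 0.55, w3 = 0.36, so the path is 0.55 × .40 + 0.36 × 0 = 0.22 against a 1-month difference of 0. The weight w2 can also be negative. With a linear control change and a delayed effect (D2 = 0, D3 = .40), w3 = 1.08 and the path is about 1.08 × .40 = 0.43, above the 1-month difference.

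**4. Size under assumed inputs.** Population maximum-likelihood fits; SD 1, 1:1 allocation, complete data, seven correlation structures (correlations .4 to .75), both conditional versions. Arm difference at 2 weeks → 1 month, then the path in outcome SDs:
- 0.30 → 0: 0.15-0.21 with control +0.3 or +0.4 at both visits; 0.08-0.10 with control +0.1.
- 0.30 → 0.15: 0.21-0.24 and 0.19-0.20 respectively, so 0.06-0.09 and 0.04-0.05 above the 1-month difference.
- 0.15 → 0.30: 0.24-0.28 and 0.29-0.30 respectively.
- 0 → 0.30: 0.22-0.33 with control +0.3 or +0.4; 0.30-0.35 with control rising linearly (+0.15, then +0.30).
- 0.30 → 0.30 with control flat after 2 weeks (proportional), or any of these growing or half-fading patterns with an unchanged control arm: exactly the 1-month difference.

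**5. How good a check is conditional-model fit?** For a correct model, RMSEA ≥ .08 when chi-square ≥ df + df·N·.0064.
- N = 60: thresholds 1.384 (df 1) and 2.768 (df 2); probabilities 24% and 25%.
- N = 200: thresholds 2.28 and 4.56; probabilities 13% and 10%.

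In the other direction, at N = 200 with control +0.3 or +0.4, RMSEA flags the full fade in 39-78% of trials and the half fade in 17-35%. These rates are for RMSEA alone, not for the four indices together. N is assumed.

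**The case against.** The strongest reply is that the plan makes neither claim. It tests treatment on the slope factor, never labels the path a 1-month effect, and never says that good fit proves the trajectories. Fit indices at df = 0 change no estimate or p-value. The fit rule is not limited to the unconditional model, so it already reaches the conditional one, where its df tests the shared time course. Zero df also rests on silence: a short plan may simply not mention equal residual variances.

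Much of this stands. The slope test is valid for its own target, and a significant path when an effect fades reflects a real difference in trajectory. A reader might infer that such a result would be a false positive, or that the plan misreports a 1-month effect; the text supports neither. Nor can one say that the whole fit rule is empty, since the conditional model is testable, if weakly. A general claim that growing effects are attenuated also fails: the path for a delayed effect can fall on either side of the 1-month difference.

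Three further cautions hold. The size of the distortion depends heavily on the assumed control change. The figures are in outcome SDs, whereas the plan's coefficient is scaled by the latent slope SD; in some half-fade cells the unbounded slope variance was negative, and there that coefficient does not exist. Multiple imputation was not simulated.

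What remains is that the plan applies one fit rule to two kinds of model without giving df or constraints. It also offers no direct visit contrast against which to read the path.

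**Conclusion.** The point holds in a limited form and concerns reporting more than design. As written, the unconditional model has df = 0, so the RMSEA, SRMR and CFI cut-offs cannot fail for any of at least 8 outcomes; an unstated equal-variance constraint would change this to df = 2. That result needs only the stated loadings, three waves and free variances.

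The slope path remains a legitimate trajectory test but should not be read as the 1-month effect unless the arms' courses are proportional. The Control PFI has active smoking content and only the Active PFI adds exercises to keep practising, so neither an unchanged control arm nor proportional courses can be presumed. The gap may be a few hundredths of an SD or, for a fully faded effect, up to about 0.2 SD. Its size and direction rest on arm means and correlations that the documents do not give.

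**What to change.** 1. State the residual- and factor-variance constraints and the df of each model. Do not offer the cut-offs as evidence for a just-identified unconditional model. Report chi-square, df and fit indices separately for the conditional model, say whether treatment also predicts the intercept, and say how fit statistics are combined over the imputed datasets. Note that the RMSEA cut-off is itself unreliable at 1-2 df.

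2. From the same imputed datasets, report baseline-adjusted arm differences with confidence intervals at 2 weeks and at 1 month (arm-by-visit means, unstructured covariance) beside the slope path. Present them as supportive estimates, not as further hypothesis tests. Keep the slope path as the trajectory test, and rest any statement about the 1-month effect on the direct 1-month contrast.

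The cost is one extra model per outcome and no new data. If the shared course holds, the direct contrast is somewhat less precise than the slope-only path. At an assumed 100 per arm and a 0.3 SD effect, power is 0.64-0.76 against 0.64-0.83, with a largest loss of 0.09. Against the version in which treatment also predicts the intercept (0.50-0.73) there is no loss.

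### The effect size the plan calls Cohen's d is scaled by the SD of the latent slope, not of the outcome, so the 0.2/0.5/0.8 labels do not carry over to it

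*Combined protocol and SAP*

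**What the plan says.** The Statistical Analysis Plan fits one growth model per outcome: "Latent growth curve (LGC) analyses were then conducted using Mplus version 8.6 using maximum likelihood". A conditional model is then used to "examine the impact of treatment (0 = Control PFI, 1 = Active PFI) on the slope factor for each of the stated outcome variables". On the time scores it states that "shape factors were set for the slope to be centered at the baseline assessment and the 1-month follow-up was fixed at 1.0", and adds: "The 2-week follow-up was freely estimated". Effect sizes are "interpreted in the Cohen's d metric (i.e., small = 0.2, medium = 0.5, and large = 0.8) utilizing the partially standardized path coefficient".

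The plan does not name the SD used in the standardization. It gives no step for re-expressing the path in SDs of the observed outcome, and it reports no outcome or slope variances.

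**The concern.** The dependent variable of the treatment path is a latent variable, the slope. With the baseline loading at 0 and the 1-month loading at 1.0, the slope is each participant's true change from baseline to 1 month. A partially standardized path from a binary predictor is a mean difference in SDs of its dependent variable, so here the unit is the SD of true change. Cohen's d as readers will understand it for motivation, smoking rate or distress tolerance is in SDs of that outcome.

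The SD of true change depends on how reliably the outcome is measured, how strongly baseline and 1-month values correlate, and how the spread differs between the two times. These will vary across the smoking and mood outcomes. Two outcomes with the same effect in outcome SDs can therefore receive different labels, and the values cannot be set beside d from other trials. The labels are the plan's only stated rule for judging the size of an effect, and they apply to every outcome.

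**Working it through.** **Inputs from the Statistical Analysis Plan.** Treatment coded 0/1; treatment path onto the slope; loadings 0 at baseline, free at 2 weeks, 1.0 at 1 month; labels at 0.2, 0.5 and 0.8. The documents state no effect size, SD, reliability, correlation or slope variance, so there is no figure of the plan's own to reproduce.

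**Assumptions, none from the documents.** 1:1 allocation; within-arm outcome SD of 1 at both times; reliability R; baseline-to-1-month correlation r; measurement errors uncorrelated over time.

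**Step 1: the two quantities.** Let b be the unstandardized path, that is, the arm difference in 1-month change in outcome units, and v the within-arm slope variance. Under 1:1 allocation the total slope variance is v + b²/4. Then:

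- partially standardized path = b / √(v + b²/4)
- d on the outcome scale = b / SD(outcome) = b when that SD is 1

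So path = d / √(v + d²/4).

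**Step 2: dependence on slope variance.** With v as a fraction of the baseline outcome variance:

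| v | 0.05 | 0.1 | 0.2 | 0.3 | 0.5 | 1.0 | 1.5 |
|---|---|---|---|---|---|---|---|
| path when d = 0.2 | 0.82 | 0.60 | 0.44 | 0.36 | 0.28 | 0.20 | 0.16 |
| path when d = 0.5 | 1.49 | 1.24 | 0.98 | 0.83 | 0.67 | 0.49 | 0.40 |
| d when path = 0.5 | 0.12 | 0.16 | 0.23 | 0.28 | 0.37 | 0.52 | 0.63 |

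**Step 3: tying v to R and r.** True-score variance is R at each time and the covariance between times is r, so v = R + R − 2r = 2(R − r). Apart from the small d²/4 term, path and d agree at r = R − 0.5. The path is larger than d above that correlation and smaller below it. At R = 0.8:

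| r | 0.2 | 0.3 | 0.4 | 0.5 | 0.6 | 0.7 |
|---|---|---|---|---|---|---|
| v = 2(R − r) | 1.2 | 1.0 | 0.8 | 0.6 | 0.4 | 0.2 |
| path, d = 0.20 | 0.18 | 0.20 | 0.22 | 0.26 | 0.31 | 0.44 |
| path, d = 0.30 | 0.27 | 0.30 | 0.33 | 0.38 | 0.46 | 0.64 |
| path, d = 0.50 | 0.44 | 0.49 | 0.54 | 0.61 | 0.74 | 0.98 |
| true d that earns *large* | 0.96 | 0.87 | 0.78 | 0.68 | 0.55 | 0.39 |

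For example, d = 0.20 at r = 0.7 gives 0.20/√(0.2 + 0.01) = 0.20/√0.21 = 0.436. The last row is d = 0.8√v / √(1 − 0.8²/4).

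**Step 4: a wider grid.** Take R = 0.7, 0.8 and 0.9, with r from 0.2 to R − 0.1 in steps of 0.1 (5 + 6 + 7 = 18 cells). At d = 0.20 the path exceeds d in 12 cells (ratio 1.11 to 2.18), is within 1% in 3 and falls below in 3 (ratio 0.84 to 0.91). The tally depends on d: at d = 0.50 it is 12 above and 6 below.

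**Step 5: simulation.** The conditional growth model with a free 2-week loading was fitted by maximum likelihood to 400,000 simulated participants with d = 0.20 and R = 0.8. The path came out at 0.18, 0.20, 0.26, 0.32 and 0.44 for r = 0.2, 0.3, 0.5, 0.6 and 0.7, while b divided by the baseline SD stayed at 0.20 throughout. A separate simulation with v = 0.1 gave a baseline-SD d of 0.20 and a path of 0.61, against 0.60 from the formula.

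**The case against.** The partially standardized path is a legitimate standardized mean difference: it expresses the treatment effect in SDs of the variable being modelled, and as such it can be compared across outcomes in SDs of latent change. On this view the fault is only an unnamed standardizer placed beside conventional cut-offs. That describes the path correctly, but the plan does more than leave the unit unnamed. It calls the result Cohen's d and attaches the outcome-SD labels.

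Four further points stand as limits:

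- **The standardizer is inferred.** The inference follows from the stated model and the usual meaning of partial standardization. If another SD was meant, the plan needs the same clarifying sentence.
- **The size is illustrative.** In the table at R = 0.8, a true 0.20 never reaches *medium*. The upward relabelling of 0.30 to *medium* and of 0.50 to *large* needs R − r below about 0.17. Nothing in the documents shows where any outcome lies.
- **Equal SDs are assumed.** If the baseline and 1-month SDs differ, their ratio also affects the discrepancy, so the table may not describe outcomes used for screening.
- **No decision hangs on a label.** The documents tie no success criterion or sample size to one, and inference on the treatment path is untouched.

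A fair point about the remedy is that a baseline SD narrowed by screening would inflate d. The fix below allows for this.

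**Conclusion.** The concern holds. Following the plan as written yields a figure in SDs of latent change and reports it as Cohen's d. How far it departs from d, and in which direction, cannot be determined from the documents. Under equal SDs and 1:1 allocation, with reliability 0.7 to 0.9 and correlations from 0.2 up to 0.1 below the reliability, a true d of 0.20 is multiplied by between 0.84 and 2.18. The conclusion itself does not rest on those assumptions. It needs only that the standardizer is the slope SD and that this SD generally differs from the outcome SD.

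The damage is confined to effect-size values and their labels. It should be fixed because those labels cover every outcome and the correction is easy.

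**What to change.** Amend the effect-size sentence in the Statistical Analysis Plan so that:

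1. d is the unstandardized treatment-on-slope coefficient divided by the pooled within-arm SD of the observed outcome at baseline, with a 95% CI. The 0.2/0.5/0.8 labels apply only to this figure.
2. For smoking rate and distress tolerance, d on the pooled within-arm 1-month SD is shown as well. The RCT Procedure uses "selected eligibility screening questions (e.g., cigarettes smoked per day, distress tolerance" at entry, which may narrow the baseline spread. If the baseline SD were 0.9, 0.8 or 0.7 of the 1-month SD (assumed), a d of 0.20 on the 1-month SD would become 0.20/0.9 = 0.22, 0.20/0.8 = 0.25 or 0.20/0.7 = 0.29 on the baseline SD. Where the two values fall on different sides of a cut-off, the report should say so.
3. If the partially standardized path is kept, it is described as SDs of the latent slope, carries no Cohen labels, and is omitted when the estimated slope variance is not positive.

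The cost is one or two sentences and one division per outcome, two for the screened outcomes. The CI takes a little more work, because it should reflect uncertainty in the SD and be combined across the imputed datasets. No new data or model is needed. Some reported effect sizes may become smaller, and the two denominators may disagree for the screened outcomes.
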